13 STATISTICAL METHODS

13.1 Determination of Sample Size

This study is designed to test non-inferiority of lasmiditan doses relative to placebo, with an alprazolam test versus placebo to confirm the sensitivity of the simulator to detect treatment effects. The following assumptions were made in the sample size computation: (a) within-subject standard deviation for SDLP is approximately 6 cm; (b) the true difference between lasmiditan doses and placebo is 0; and, (c) the non-inferiority (NI) margin is proposed to be

4.4 cm, which is the effect seen with 0.05% of BAC. Under these assumptions, a sample of 80 subjects would provide in excess of 90% power to establish non-inferiority of any given dose of lasmiditan compared to placebo in terms of the primary end point, SDLP. This sample size is considered more than adequate to detect alprazolam differences from placebo, which are anticipated to exceed the NI margin.

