4. STUDY ENDPOINTS

Primary Endpoint

The primary endpoint for this study is simulated driving performance as measured by SDLP using the CRCDS-MiniSim.

Secondary Endpoints

The secondary endpoints for this study include other measures of simulated driving performance, KSS and CogScreen SDC test.

- Sleepiness Endpoint – KSS
- Self-reported readiness to drive (“Right now do you feel safe to drive?”)
- Visual Analog Scales (VAS) to assess subject’s motivation and self-appraisal of their driving performance
- Performance Endpoints
 - CogScreen SDC test
 - Number of correct responses
 - Response Accuracy
 - Standard deviation of reaction time
- Driving Performance Endpoints
 - Lane exceedance; including number, maximum, duration, and area of exceedance
 - Ratio above speed limit, excessive speed count, excessive speed ratio
 - Average speed, speed deviation, speed count, speedings ratio
 - Excessive Ay (cornering speed threshold exceeded)
 - Collision count, off-road crashes, total collisions
 - DA: Correct Responses, Omission Errors, Commission Errors, Reaction Time, Standard Deviation of Reaction Times
- Single-dose plasma drug levels and driving performance

Safety Endpoints

Safety endpoints include:

- Adverse Events
- Clinical Laboratory Tests (hematology, chemistry, urinalysis)
- Vital Signs
- Physical examination
- Concomitant medication
- ECGs
- C-SSRS

The details of the safety endpoints’ assessment are presented in [Section 10](#).

Pharmacokinetic Endpoints

The pharmacokinetic endpoint for this study is plasma lasmiditan concentration data.

Sample Size Determination

This study is designed to test non-inferiority of lasmiditan doses relative to placebo, with an alprazolam test versus placebo to confirm the sensitivity of the simulator to detect treatment effects.

The following assumptions were made in the sample size computation:

- (a) within-subject standard deviation for SDLP is approximately 6 cm;

(b) the true difference between lasmiditan doses and placebo is 0;

(c) the non-inferiority (NI) margin is proposed to be 4.4 cm, which is the effect seen with 0.05% of blood alcohol content (BAC).

Under these assumptions, a sample of 80 subjects would provide in excess of 90% power to establish non-inferiority of any given dose of lasmiditan compared to placebo in terms of the primary end point, SDLP. This sample size is considered more than adequate to detect alprazolam differences from placebo, which are anticipated to exceed the NI margin.

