9. PHARMACOKINETICS AND PHARMACODYNAMIC ANALYSIS

Pharmacokinetic Analysis

Blood samples for the determination of plasma lasmiditan concentrations will be drawn at the following time points following each dose:

- Days 1, 7, 14, 21, and 28 pre-dose (within 30 minutes prior to dose) of each period
- Days 1, 7, 14, 21, and 28 of each period at 155 minutes (-15 to +30 minutes) after dosing

A summary table will be provided summarizing each time point by treatment.

Pharmacodynamic Analysis

Primary Analysis:

The primary endpoint, SDLP, will be analyzed using a normal theory mixed effects model with fixed effects for sequence, period, and treatment, and a random effect for subject within sequence. A variance component covariance structure and Kenward-Roger degrees of freedom will be used.

Pair-wise comparisons (hypothesis tests) of differences in means, and 95 % confidence intervals on differences will be provided for:

1. Lasmiditan 50 mg versus placebo
2. Lasmiditan 100 mg versus placebo
3. Lasmiditan 200 mg versus placebo
4. Alprazolam 1.0 mg versus placebo
5. Lasmiditan 50 mg versus alprazolam 1.0 mg
6. Lasmiditan 100 mg versus alprazolam 1.0 mg
7. Lasmiditan 200 mg versus alprazolam 1.0 mg

In addition, pair-wise within-subject differences in SDLP greater than 4.4 cm in absolute value (equal to the previously found difference between placebo and 0.05% BAC for the CRCDS) will be compared using McNemar (MM) test. Furthermore, these pair-wise, within subject differences in SDLP will be tested for symmetry about zero (Laska 2012) using the maximally selected McNemar test.

Summary statistics will be provided (mean, SD, median, minimum, maximum) for SDLP for each time point and treatment group. Figures will be provided for the within subject difference scores by treatment and day as both a histogram and scatter plot. Data listings for driving simulator data will be provided.

Secondary Analyses Performed as the Primary Analysis:

Secondary endpoints of VAS, SDC, and driving performance endpoints will be evaluated and presented similarly, however Lane Exceedance will be log transformed (more specifically $\ln(x+1)$) prior to analyses.

Tables will be presented in the same format as the primary output for:

- Visual Analog Scales (VAS) to assess subject's motivation and self-appraisal of their driving performance
- KSS
- Performance Endpoints
 - CogScreen SDC test
 - Number of correct responses

- Response Accuracy
 - Standard deviation of reaction time

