- Driving Performance Endpoints
 - Lane exceedance; including number, maximum, duration, and area of exceedance
 - Ratio above speed limit, excessive speed count, excessive speed ratio
 - Average speed, speed deviation, speed count, speedings ratio
 - Excessive Ay (cornering speed threshold exceeded)
 - DA: Correct Responses, Omission Errors, Commission Errors, Reaction Time, Standard Deviation of Reaction Times

A data listing for the two VASs and SDC results will be provided

Additional Secondary Analyses:

Driving Performance Collision count, off-road crashes, Total Collisions:

Summary statistics will be provided (mean, SD, median, minimum, maximum) for collision count, off-road crashes, and total number of collisions for each time point and treatment group. Additionally, differences in number of collisions/crashes for each pair-wise comparison will be provided with their corresponding Wilcoxon Signed Rank p-value. A bar chart will be provided pooling total number of collisions by 0, 1, 2, or >=3 for all 3 treatment groups.

Self-reported readiness:

Pair-wise comparisons for readiness to drive will be analyzed using McNemar's test. A bar graph for percentage of subjects reporting not safe to drive will be reported by treatment and day.

Plasma drug levels:

The decision as to which plasma samples collected will be assayed for evaluation of pharmacokinetics will be determined by CoLucid Pharmaceuticals, Inc. The correlations between single-dose plasma drug concentrations the morning of the driving simulation and the primary and key secondary end points will be evaluated, data permitting. If indicated, these samples may also be assayed and/or pooled for assay in an exploratory manner for metabolites and/or additional pharmacodynamic markers.

The relationship between single-dose drug levels and all secondary endpoints (excluding self-reported readiness) will be assessed by correlation. Both the Spearman and Pearson correlations will be reported. Figures will be provided for the within subject difference from placebo scores by treatment and day as a scatter plot.

Statistical Analysis

Initially, the statistical significance of alprazolam vs. placebo ($p < 0.05$) comparison for SDLP is necessary to validate the experiment as having the ability to detect effects (i.e., assay sensitivity).

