To address multiplicity of testing, for the primary endpoint of SDLP, ascending doses of lasmiditan will be interpreted in a sequential manner, starting with the 50 mg dose and proceeding to 100 mg and then 200 mg. Doses of lasmiditan will be considered non-inferior to placebo if the upper 95% confidence limit on the difference in SDLP between that dose and placebo is less than 4.4 cm and lower doses also do not exceed the NI margin. No adjustment to alpha levels will be made for either the comparison of alprazolam to placebo or to lasmiditan, or for secondary endpoints or analyses. Formal statistical tests (where performed) will be two-sided and testing at the $\alpha = 0.05$ level of significance.

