{Repeat table for VAS Motivation (Table 14.2.2.1), VAS self-appraisal (Table 14.2.2.2), SDC number of correct responses (Table 14.2.3.1), SDC Accuracy (Table 14.2.3.2), SDC Standard deviation of reaction time (Table 14.2.3.3), Driving Performance Lane Exceedance number (Table 14.2.4.1), maximum (Table 14.2.4.2), duration (Table 14.2.4.3) area of exceedance (Table 14.2.4.4), ratio above speed limit (Table 14.2.4.5), excessive speed count (Table 14.2.4.6), excessive speed ratio (Table 14.2.4.7), average speed (Table 14.2.4.8), speed deviation (Table 14.2.4.9), speed count (Table 14.2.4.10), speedings ratio (Table 14.2.4.11), excessive ay (cornering speed threshold exceeded) (Table 14.2.4.12), Driving Performance Divided Attention - Correct Responses (Table 14.2.4.16), omission errors (Table 14.2.4.17), commission errors (Table 14.2.4.18) reaction time (Table 14.2.4.19), standard deviation of reaction time (Table 14.2.4.20)}

*Mixed effects model with fixed effects for sequence, period, and treatment, and a random effect for subject within sequence, variance component covariance structure, and Kenward-Roger degrees of freedom. Estimated differences are first treatment label listed minus second treatment label.

SAS Program Name:

Date:

Source Data: Listing 16.2.6.X

Table 14.2.1.2.1
Standard Deviation of Lateral Position (SDLP) Analysis of Symmetry about Zero (ITT Population - Alprazolam versus Placebo)
(ITT Population)

Threshold	Sign	Low	Neutral	High	McNemar	Nominal P-value
x.xxx	-/+	xx	xx	xx	x.xxxx	0.xxxxxxx
x.xxx	-/+	xx	xx	xx	x.xxxx	0.xxxxxxx

Repeat table for other comparisons.

Maximally selected McNemar's test statistic (MM) Critical value for n=XX paired differences, at alpha=0.05 (two-tailed) is X.XXX.

Symmetry about zero is rejected if the maximum of the McNemar's test statistics is greater than X.XXX.

If the sum of the high and low values is less than 25, an exact two-sided p-value is computed using the binomial distribution (p=1/2), conditional on the sum of the high and low values (as 2 X the one-sided p-value).

SAS Program Name:

Date:

Source Data: Listing 16.2.6.1.X

Table 14.2.4.13
Driving Performance Collision Count
(ITT Population)

Statistic	Placebo (N=xx)	Lasmiditan 50 mg (N=xx)	Lasmiditan 100 mg (N=xx)	Lasmiditan 200 mg (N=xx)	Alprazolam 1 mg (N=xx)
N	xx	xx	xx	xx	xx
Mean	x.x	x.x	x.x	x.x	x.x
SD	x.xx	x.xx	x.xx	x.xx	x.xx
Median	x.x	x.x	x.x	x.x	x.x
Min, Max	xx, xx	xx, xx	xx, xx	xx, xx	xx, xx

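### Must the alprazolam assay-sensitivity test be tied to the 4.4 cm margin, given that p<0.05 can be met by an effect whose upper limit is below it?

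*SAP*

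**What the plan says.** SAP section 9 (Statistical Analysis) opens with the validity condition: significance at p<0.05 of the alprazolam-versus-placebo "comparison for SDLP is necessary to validate the experiment as having the ability to detect effects (i.e., assay sensitivity"). The next paragraph adds "Formal statistical tests (where performed) will be two-sided", at the 0.05 level, and "No adjustment to alpha levels will be made for either the comparison of alprazolam to placebo or to lasmiditan". The margin enters through a separate rule for the test drug only: "Doses of lasmiditan will be considered non-inferior to placebo if the upper 95% confidence limit on the difference in SDLP" from placebo is below 4.4 cm and the lower doses also pass.

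The protocol gives alprazolam the task of confirming that the simulator can detect treatment effects, but sets no decision rule. Alprazolam and 4.4 cm meet in two other places. Protocol section 13.1 states "This sample size is considered more than adequate to detect alprazolam differences from placebo, which are anticipated to exceed the NI margin", and SAP section 4 repeats it. SAP section 9 also adds a McNemar comparison of "pair-wise within-subject differences in SDLP greater than 4.4 cm in absolute value". Neither is made a condition of validity.

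**The concern.** In a non-inferiority comparison, poor sensitivity helps the sponsor because it pulls every difference towards zero. The positive control guards against that. The margin is described as the effect of 0.05% blood alcohol, so one would like to know that this experiment could have shown an effect of that size.

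As written, alprazolam could validate the trial with a result that would itself count as non-inferior to placebo. A lasmiditan claim at 4.4 cm would then rest on an experiment that also bounded a sedating drug below 4.4 cm. How to read that would be left until the results were known. In addition, a two-sided test with no stated sign is formally met if alprazolam improves driving.

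**Working it through.** **Inputs.** "within-subject standard deviation for SDLP is approximately 6 cm" (SAP section 4), read as the per-period residual SD; 80 completers; margin 4.4 cm; two-sided 95% limits. Residual degrees of freedom with complete data: 400 − 80 − 4 − 4 = 312, so t = 1.968.

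**The plan's own figure.** SE = 6 × √(2/80) = 0.949 cm. Non-inferiority power at a true difference of 0 is Φ(4.4/0.949 − 1.968) = 99.6%, which agrees with the stated figure of more than 90%.

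**The window.** The half-width is 1.968 × 0.949 = 1.867 cm. Significance in the harmful direction needs an estimate above 1.87 cm. An upper limit below 4.4 cm needs an estimate below 4.4 − 1.867 = 2.53 cm. Both hold between 1.87 and 2.53 cm. For example, an estimate of 2.2 cm has a 95% CI of 0.33 to 4.07 and p = 0.021.

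**How likely it is** (normal estimate, SD 6 cm):

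| True alprazolam effect (cm) | Chance of falling in the window |
|---|---|
| 2.2 | 27% |
| 2.5 | 26% |
| 3.0 | 20% |
| 4.4 | 2.1% |
| 5.0 | 0.4% |

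The SD matters, and values other than 6 cm are assumptions. At SD 5 the window is 1.56 to 2.84 cm. At SD 7 it is 2.18 to 2.22 cm. It closes at 2.2/(1.968 × √(2/80)) = 7.07 cm. If 6 cm is instead the SD of the paired difference, the window is 1.34 to 3.07 cm, with a chance of 80% at a true effect of 2.2 cm but still about 2% at 4.4 cm.

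**Direction.** A significant result in the wrong direction has probability of about 2.5% at a true effect of 0 and 0.1% at 1 cm.

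**What a margin-linked condition would do.** Suppose alprazolam's upper limit also had to be at least 4.4 cm, so that the estimate had to reach 2.53 cm. Take one lasmiditan dose with a true difference of 0 and a correlation of 0.5 between the two contrasts from the shared placebo mean. The chance of passing both the validity condition and non-inferiority is:

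| SD (cm) | True alprazolam effect (cm) | Current rule | With the extra condition |
|---|---|---|---|
| 6 | 2.5 | 74% | 48% |
| 6 | 3.0 | 88% | 68% |
| 6 | 3.5 | 95% | 84% |
| 6 | 4.4 | 99.2% | 97.2% |
| 5 | 3.0 | 97% | 58% |

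The loss is nearly equal to the window probability (74 − 48 = 26 points, against 26% above). A harmless dose almost always passes non-inferiority, so almost every trial in the window is a valid conclusion given up.

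Now assume that sensitivity is halved, with alprazolam showing 2.5 cm and a dose showing 2.2 cm at SD 6; the documents do not give this case. The chance that the dose passes falls from 42% to 23%, a gain of 19 points, and the extra condition itself is still met in 49% of trials (75% under the current rule).

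**Precision.** With alprazolam at 3.0 cm and a harmless dose, the extra condition succeeds in 58% of trials at SD 5, but in 72% at SD 7 (74% if the variance is taken as known). Better data do worse, and above SD 7.07 cm the condition has no effect.

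**What the plan already shows.** Comparisons 5 to 7 in SAP section 9 set each lasmiditan dose against alprazolam with a 95% CI, in the same table as the placebo comparisons (shell of Table 14.2.1.1). In the halved-sensitivity case, 89% of the trials that pass the current rule and non-inferiority would show lasmiditan not significantly better than alprazolam. With a harmless dose and alprazolam at 2.5 cm, that share is 17%.

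**The case for a change.** The best argument for a change is that an assay-sensitivity check exists for the case where the expectation about alprazolam fails, so a low probability under that expectation is no comfort. A p-value against zero shows that some effect was detected, not that one near the margin could be. If the simulator was blunted, losing a non-inferiority conclusion is no loss. If alprazolam behaves as expected, the extra condition costs about 2 points at most. Settling the reading in advance also avoids an argument after the results are known.

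Much of this stands: the text has no such condition, the arithmetic is right, and a reading fixed beforehand is better than one fixed afterwards. The proposed condition, however, cannot separate a blunted simulator from a smaller true effect of alprazolam 1 mg. In the second case the lost conclusions are real, and a significant effect of about 2.2 cm arguably shows that the experiment resolved half the margin. The 2-point cost applies only at true alprazolam effects of 4.4 cm or more, where the condition is hardly needed; where it acts, the cost is 11 to 26 points at SD 6 for true effects of 3.5 down to 2.5 cm.

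Nor does the plan contradict itself. Section 13.1 of the protocol states an expectation, while the SAP states a necessary condition for detecting effects. It does not call that condition sufficient.

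**Conclusion.** No change to the plan is needed. The validity condition is a conventional detection test. Its missing direction is supplied by the words positive control and by the stated aim of detecting residual sedation, and no analyst would count an improvement on alprazolam as validation. The missing link to 4.4 cm is a fair trade-off: a hard condition would cost up to about 26 points of valid conclusions at SD 6, and 39 points at SD 5 with a true alprazolam effect of 3.0 cm, and it would be easier to pass with noisier data.

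The awkward outcome has a probability of about 2% or less if alprazolam's true effect is at or above the margin, as the plan anticipates. If it does occur, the planned alprazolam-placebo interval and comparisons 5 to 7 will usually show it, and a competent report would discuss them against 4.4 cm.

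This rests on 80 completers, a residual SD near 6 cm and the plan's expectation for alprazolam. If the true effect were only 2 to 3 cm, the chance of the outcome would be 20 to 27% at SD 6 and 39 to 59% at SD 5, and the interpretation would then depend on those intervals.

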10. SAFETY

Adverse Events

An AE is defined as any untoward medical occurrence in a subject administered a medicinal product and which does not necessarily have to have a causal relationship with this treatment. An AE can therefore be any unfavorable and unintended sign (for example, an abnormal laboratory finding), symptom, or disease temporally associated with the use of a medicinal product, whether or not considered related to this medicinal product.

A suspected adverse reaction is any AE for which there is a reasonable possibility that the drug caused the AE. 'Reasonable possibility' means there is evidence to suggest a causal relationship between the drug and the AE. A suspected adverse reaction implies a lesser degree of certainty about causality than adverse reaction, which means any AE caused by a drug.

AEs occurring after the initiation of the treatment are referred to as treatment emergent adverse events (TEAEs).

TEAEs will be assigned to a treatment based on the time of occurrence in relation to the last treatment administered prior to the onset of the TEAE. TEAEs will be assigned using the following rules:

- TEAE will be assigned to the last treatment taken by the subject where the date and time of the last treatment dosing is on or before of the start date and time of the event. Such assignment will be performed irrespective of any washout period between the start and stop dates of the TEAE.
- Any TEAE started after the discharge and during the follow-up period will be assigned to the last treatment that the subject has taken during last period.

As an overall summary of AEs, the following will be presented by treatment and overall:

- Number of reported AEs;
- Number of reported TEAEs;
- Number and percentage of subjects experiencing TEAEs;
- Number and percentage of subjects experiencing a drug-related TEAE (i.e. those with a relationship classified as reasonable possibility)
- Number and percentage of TEAEs by relationship to study treatment (i.e. reasonable possibility, no reasonable possibility);
- Number and percentage of TEAEs by severity;
- Number of reported SAEs (serious adverse events);
- Number and percentage of subjects experiencing SAEs;
- Number and percentage of subjects experiencing drug-related SAEs;
- Number and percentage of TEAEs leading to withdrawal; and
- SAEs with an outcome of death.

Frequency tables will be presented by treatment, system organ class and preferred term that summarize all Treatment Emergent Adverse Events (TEAEs), and SAEs. Frequency tables will also be presented by treatment, system organ class, preferred term and maximum severity and by treatment, system organ class, preferred term and relationship to study drug.

Subject listings of all Adverse Events (AEs) including severity and relationship to study drug will be provided. AEs leading to withdrawal and SAEs will also be presented in separate listings.

Concomitant Medications

Medications taken after the first dose of study drug until after discharge from the study will be recorded. Concomitant medications will be presented in a listing. The medication name, active ingredient, dose, units, formulation, route, indication or reason taken, code, date and time taken will be presented. The listing will also include the coding terms (e.g., ATC and Preferred Term).

Extent of Exposure

Details of drug dosing (actual treatment received, actual date and time of administration, dose administered, and route of administration) will be listed by subject.

Clinical Laboratory Evaluations

Planned laboratory analyses include:

- Blood Chemistry: alkaline phosphatase (ALP), alanine aminotransferase (ALT), aspartate aminotransferase (AST), total and direct bilirubin, blood urea nitrogen (BUN), creatinine, gamma glutamyltransferase (GGT), glucose, potassium, sodium;
- Hematology: hemoglobin, hematocrit; platelets, prothrombin time (PT), red blood cells (RBC), white blood cells (WBC) with differential (absolute),
- Urinalysis: bilirubin, erythrocytes, glucose, ketones, leukocytes, nitrite, pH, protein, specific gravity, urobilinogen
- Other: urine drug screen and serum pregnancy.

Hematology, chemistry and quantitative urinalysis laboratory test results, as well as the change from baseline, will be summarized by sequence, parameter and visit.

Separate listings of all individual data for urinalysis, hematology, chemistry and other laboratory tests will be presented by subject, laboratory test and visit.

Subject listings of abnormal on-study laboratory values will be provided, including demographic information. Similarly, clinically significant on-study laboratory data will be presented in a second listing.

Vital Signs

Vital signs will include the measurement of blood pressure, heart rate, oral temperature, and body weight.

For all vital signs, raw values, as well as the change from baseline, at each time point will be summarized by treatment, parameter and visit. Vital signs data will also be presented in a listing.

Subject listing of abnormal on-study vital signs values (Out-of-Range – Not Clinically Significant (NCS) or Clinically Significant (CS)) will be provided. Similarly, CS on-study vital signs values (Out-of-Range – CS) will be presented in a second listing.

Electrocardiogram

A triplicate 12-lead ECG will be obtained at time points throughout the study. In some cases, repeat abnormal ECGs may be obtained.

Raw values at each time point, as well as the change from baseline, will be summarized by sequence, parameter and visit and will also be presented in a listing.

A subject listing of abnormal on-study ECG assessments (Abnormal – NCS or Abnormal – CS) will be provided. Similarly, CS on-study ECG assessments (Abnormal – CS) will be presented in a second listing.

Physical Examination Findings

A physical examination will be conducted and results will be presented in a listing.

A subject listing of abnormal on-study physical examination results (Abnormal – NCS or Abnormal – CS) will be provided, including demographic information. Similarly, CS on-study physical examination results (Abnormal – CS) will be presented in a second listing.

Columbia-Suicide Severity Rating Scale (C-SSRS)

The Columbia-Suicide Severity Rating Scale (C-SSRS) is a suicidal ideation rating scale. The scale identifies behaviors and thoughts that are associated with an increased risk of suicidal actions in the future. The C-SSRS will be performed at Screening, on Days -1, 6, 13, 20, and 27, and Day 35 or EOS.

Subjects who answer 'Yes' to any of the questions on the C-SSRS questionnaire will be presented in a listing

Epworth Sleepiness Scale

The Epworth Sleepiness Scale assessment will be performed at Screening and results will be presented in a listing.

Simulator Sickness Questionnaire

A simulator sickness questionnaire will be performed at Screening and results will be presented in a listing.

